1. **Sociodemographic Questionnaire:** Sociodemographic information will be obtained at the pre-randomization time point consisting of questions concerning age, gender, ethnicity, education, employment history, marital status and household composition, and religious affiliation and practices. Significant medical and other life events which occur during the course of treatment and follow-up will be recorded for each patient. (5 minutes; T0)
2. **Distress Thermometer (DT):** The Distress Thermometer (Roth et al., 1998) is a single-item visual analog scale used to screen cancer patients for the presence of psychological distress with a 0-10 range. The National Cancer Center Network (NCCN) Clinical Practice Guidelines for Distress Management recommend use of the DT, along with a 34-item problem checklist (NCCN, 2003, 2009). An extensive research literature has documented the utility of the DT as a screening tool for oncology settings, and has identified a cut-off of 4 or greater for identifying clinically significant psychological distress (e.g., Grassi et al., 2009; Jacobsen et al., 2005). (2 minutes; T0, T2, T3)
3. **Karnofsky Performance Rating Scale (KPRS):** Observer-rated scale used by physicians to report patient's level of physical performance with a range of 0-100. (Karnofsky & Buchenal, 1949; Coscarelli-Schag, 1984). KPRS is rated upon admission screening and at each assessment. (1 minute; T0, T3, T4)

Health Status Measures:

1. Health Status Interview (HS): Extent of disease, degree of medical co-morbidity, concomitant therapies, and significant medical events occurring during the study will be recorded for each patient. (5 minutes; T1)

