11.0 BIOSTATISTICS

This project involves a parallel-arm randomized controlled clinical trial to compare the efficacy of three psychotherapy interventions: 1) Individual Meaning-Centered Psychotherapy (IMCP); 2) Supportive Individual Psychotherapy (ISP); and 3) Enhanced Usual Care arm (EUC). We plan to recruit altogether 414 patients (138 in each arm) with solid tumors with advanced disease. The primary outcomes include assessments of meaning (LAP-R), spiritual well-being (FACIT-Sp) and psychological distress (HADS, SAHD, HAI, MQOL).

Omnibus MANOVA for the primary aim:

The general paradigm for assessing the outcomes will be multivariate analysis of variance (MANOVA). MANOVA is appropriate because the primary psychosocial outcomes are highly correlated. The MANOVA method essentially combines the multiple dependent variables together into a weighted linear combination of canonical variates. The canonical coefficients provide the weights in this linear combination. The canonical weights have several advantages. The main advantage is that they inform the relative contribution of each outcome to the overall canonical function (i.e., whether or not meaning contributes more than spiritual well-being to the overall canonical function). MANOVA was chosen, rather than, for example, a mixed-effects modeling approach, primarily because of these considerations. In MANOVA, the combined canonical variate is analyzed in a manner similar to a univariate ANOVA.

The primary aim of this study will be evaluated in one omnibus, one-way MANOVA model against the null hypothesis that all three randomized arms entail comparable post-intervention outcomes in meaning, spiritual well-being, and psychological distress. Thus, the dependent variables will be the six primary outcome assessments (LAP-R, FACIT-Sp, HADS, SAHD, HAI, and MQOL) measured at the post-intervention time point (week 7). The sole independent variable is the randomized intervention assignment. Dunlop, Cortina, Vaslow & Burke (1996) showed that this method provides the most generalizable findings, findings that do not depend on the patients' baseline scores or other baseline characteristics. Thus, the omnibus MANOVA will test whether or not the psychotherapy groups differ in all six correlated outcomes of interest.

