Output:	Noncentrality parameter λ	= 20.8000000
	Critical F	= 2.9936309
	Sample size	= 104
	Actual power	= 0.8062691
	Pillai V	= 0.1666667

A sample size of 104 per randomization arm (138 at baseline) at post-intervention would accommodate a post-intervention attrition rate of up to 25%, which is within the attrition rate in our pilot IMCP trial. The estimated sample size at the follow-up time point (week 15) is 90 participants per intervention condition.

Based on our current IMCP Group psychotherapy intervention, we are currently recruiting at a rate of 5 – 6 individuals to participate. This study involves the IMCP individual therapy, which is more flexible in terms of enrolling patients quickly and scheduling for starting of the therapy sessions. Thus we are confident that we will be able to recruit at a rate of 8 – 9 individuals per month and complete the total enrollment of 414 within the 4-year recruitment period.

Data analytic plans for the secondary aims

To examine clinical and demographic variables that may correspond to differential responses to Individual Meaning-Centered Psychotherapy (e.g., potential moderating influences such as gender, race/ethnicity, religiosity, level of pre-intervention social support, optimism, physical symptom burden, prognostic awareness, and treatment dose).

We anticipate that several socio-demographic and clinical variables will moderate the impact of IMCP. For example, we expect that level of religiosity (based on the IE-12) at the baseline/pre-intervention assessment will be inversely related to treatment response (i.e., less religious individuals will be more likely to experience benefits from this intervention than more religious individuals). We also predict that level of social support will moderate improvement, with those patients reporting higher levels of social support receiving the greatest benefits (because of the emphasis on connectedness to others as a source of meaning in the IMCP intervention). On the other hand, we expect that patients with poorer physical functioning (e.g., lower Karnofsky score), greater pain severity and overall symptom burden (MSAS Global Distress Index scores) will be less likely to benefit from the interventions, in part because unmanaged physical symptoms may impede participation.

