Analyses: Putative explanatory covariates will be identified and tested statistically using the method originally described by Baron and Kenny (1986), and more recently by MacKinnon (2008). Specifically, these will involve Multi-Variate Analysis of Covariance (MANCOVA) using the changes in the six primary outcomes (post intervention minus baseline) as a function of intervention condition, controlling as covariates the effects of gender, race/ethnicity, and baseline covariates in religiosity, social support, optimism, physical symptom burden, pain severity, and overall symptom burden. This analytic approach entails the following advantages: 1) change scores have the advantage of clearly identifiable direction of change, 2) psychosocial outcomes are measured on an interval scale (such as measures of temperature in the Fahrenheit or Celsius scales), so that change scores are less prone to problems associated with respondents using different internal psychological scales; and 3) precedence exists (Flay et al. 1995) in interventions designed for behavioral change. This method offers several advantages, both in terms of power as well as interpretation, to a traditional repeated measures design for analyzing data when both independent and dependent variables are assessed at two or more time points (Huck & McLean, 1975; Willet, 1988-9). Change score analyses will include the baseline score as a covariate if change is significantly correlated with baseline score (as is often the case).

To assess the relative impact of Individual Meaning-Centered Psychotherapy on different aspects of meaning (e.g., purpose, coherence, existential vacuum), as well as on different aspects of spiritual well-being (meaning versus faith):

Two additional MANOVA models will be carried out. In the first model, pre-post change scores of different aspects of meaning (e.g., purpose, coherence, existential vacuum) will be modeled by intervention conditions to examine the relative impact of IMCP on these outcomes. The canonical weights will be used to estimate the relative contribution of each mean components on the overall canonical function. Components of spiritual well-being will also be analyzed similarly, in a separate MANOVA model. Univariate ANOVA contrasts will be used to compare IMCP against ISP and IMCP against EUC.

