12.3 Randomization

Participants will be randomized to one of the two 7-week interventions (Individual Meaning Centered Psychotherapy or Supportive Individual Psychotherapy) or the Enhanced Usual Care. After eligibility is confirmed and immediately after consent is obtained, patients will be registered in the MSKCC Protocol Participant Registration (PPR) system and randomized using the MSKCC Clinical Research Database (CRDB), by calling the MSKCC PPR Office at [contact] between the hours of 8:30 am and 5:30 pm, Monday - Friday.

Randomization is overseen by the MSKCC Biostatistics Service. Randomization will be accomplished by the method of random permuted block, and stratified by two dichotomized variables: 1) baseline Distress Thermometer (4 through 6 vs. 7 through 10); and 2) baseline Karnofsky score (60 through 79 vs. 80 or greater).

Patients who are registered and randomized, but cannot make their scheduled session time (because of conflict or illness) will be placed on a waitlist so they can be offered a spot when they are available in the future, in the same treatment assignment as randomized.

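### The primary MANOVA leaves out the two factors that stratify randomization; adding them costs almost nothing and may recover a little precision

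*Combined protocol and SAP*

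**What the plan says.** Section 12.3 sets up permuted-block randomization within strata. The split on screening distress is given first: "stratified by two dichotomized variables: 1) baseline Distress Thermometer (4 through 6 vs. 7 through 10"). Performance status is the other factor, and its cut is written as "2) baseline Karnofsky score (60 through 79 vs. 80 or greater"). Section 4.2 has both measured at the screening assessment, before consent and randomization. The measure descriptions in Section 7.1 agree. The Distress Thermometer is scheduled at "2 minutes; T0, T2, T3", and for Karnofsky the text reads "KPRS is rated upon admission screening and at each assessment. (1 minute; T0, T3, T4").

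Section 11.0 (Omnibus MANOVA for the primary aim) tests six T3 scores in a one-way MANOVA: "The sole independent variable is the randomized intervention assignment". The reason given is generalizability: results should not hinge on "baseline scores or other baseline characteristics". The stratification is not mentioned there.

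For the moderator aim, Section 11.0 plans a "Multi-Variate Analysis of Covariance (MANCOVA) using the changes in the six primary outcomes (post intervention minus baseline) as a function of intervention condition", with a list of covariates. Neither stratification factor is on that list, although the text just before it says "we expect that patients with poorer physical functioning (e.g., lower Karnofsky score), greater pain severity and overall symptom burden" will gain less from treatment.

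**The concern.** The trial balances its arms on two factors and then analyses as if it had not. When strata predict outcome, an arm-only model leaves their variance in the error term although the design has removed it from the arm comparison. Standard errors are then somewhat too large and the test somewhat conservative.

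The stated reason does not justify the omission. In a linear model for a randomized trial, main-effect adjustment for factors fixed before randomization estimates the same average effect as the unadjusted comparison. It does not make the finding conditional on baseline status.

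What is at stake is precision in both planned contrasts, above all IMCP versus ISP, which the sample size section treats as the more important hypothesis.

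**Working it through.** **Inputs from the documents.** Alpha 0.01 two-sided, six outcomes, two groups per contrast, f² = 0.20 in the program output, 0.20 SD in the text, 138 enrolled and 104 analysed per arm (Section 11.0).

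**Assumed, because the documents give no value.** R², the share of the canonical variate's variance that the strata explain: 0, 2%, 5%, 10%. D, the standardized distance between two arms: 0.20 to 0.70.

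**Step 1: reproduce the plan's figure.** For two groups and p = 6, λ = f²·N and df = (6, N − 7). With N = 104, λ = 0.20 × 104 = 20.8, df2 = 97, critical F = 2.9936 and power = 0.8063. All match the printed output. There 104 is the total for two groups; the text uses it per arm, so the IMCP versus ISP contrast would have 208 patients.

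**Step 2: put the two effect sizes on one scale.** With equal arms f² = D²/4. The program's f² = 0.20 is D = 2√0.20 = 0.89. The text's 0.20 SD is f² = 0.01.

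**Step 3: add the strata.** λ = (208/4)·D²/(1 − R²) = 52·D²/(1 − R²). Two binary main effects take df2 from 201 to 199. At D = 0.50 and R² = 10%, λ rises from 52 × 0.25 = 13.0 to 13.0/0.90 = 14.4.

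| D | Arm only | R² = 0 | R² = 2% | R² = 5% | R² = 10% |
|---|---|---|---|---|---|
| 0.20 (plan's text) | 4.5% | 4.5% | 4.6% | 4.8% | 5.1% |
| 0.30 | 12.7% | 12.7% | 13.1% | 13.7% | 14.8% |
| 0.40 | 29.5% | 29.5% | 30.4% | 31.8% | 34.3% |
| 0.50 | 53.7% | 53.7% | 55.0% | 57.0% | 60.5% |
| 0.60 | 77.1% | 77.1% | 78.3% | 80.1% | 83.0% |
| 0.70 | 92.0% | 92.0% | 92.6% | 93.6% | 95.1% |
| 0.89 (f² = 0.20) | 99.7% | 99.7% | 99.7% | 99.8% | 99.9% |

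At R² = 10% the gain is about 2, 5, 7, 6 and 3 points at D = 0.30, 0.40, 0.50, 0.60 and 0.70, so D = 0.50 is close to the most favourable choice. At D = 0.50 the arm-only power is 53.73% and the power with uninformative strata is 53.71%: the worst cost is 0.02 point.

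**Step 4: the three-arm omnibus test, by simulation.** With 312 patients and IMCP 0.50 from both other arms, power goes from 56.0% to 57.4%, 59.5% and 63.4% at R² = 2%, 5% and 10%.

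**Step 5: type I error of the planned test, by simulation.** The arm-only omnibus test at nominal 0.01 rejects at 0.0095, 0.0091 and 0.0086 for R² = 2%, 5% and 10%. A second simulation, with permuted blocks of 6 (block size assumed) and R² applied to each outcome, gives 0.0087 and 0.0078 at 5% and 10%; with the strata in the model these become 0.0095 and 0.0101 (simulation error about 0.0007). The planned test errs only on the conservative side.

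**Step 6: why the T1 scores are a different matter.** Section 4.2 places T1 after randomization, and both it and Section 7.1 describe telling patients their arm before describing T1. Suppose the news shifts T1 by δ SD between arms and the shift is gone by T3. Adjusting for T1 then moves the contrast by about r·δ, where r is the baseline-to-T3 correlation. With assumed δ = 0.2 and r = 0.5 that is 0.10 SD, half the plan's 0.20 SD. Then λ = 52 × 0.10²/(1 − 0.25) = 0.693 with df2 = 201 − 6 − 2 = 193, and type I error is 0.019 instead of 0.010. It is 0.012 at r = 0.3 and 0.043 at r = 0.7. The T0 strata cannot be affected in this way.

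**The case against.** The strongest reply is that nothing here is an error. An arm-only analysis of a randomized trial is legitimate, the plan chose it openly with a reason, and no passage contradicts another. That stands, and it makes this a point about efficiency.

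A second reply is that the gain may not exist. Both factors are dichotomized, and eligibility restricts their range (Distress Thermometer 4 or more, Karnofsky 60 or more), so R² near zero is plausible. At either of the plan's own effect sizes the gain is negligible. This also stands. A reader might infer that the trial is certainly losing power; without an R² the documents do not support that.

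A reader might also infer that the primary model should adjust for the six baseline scores, which could well explain more variance than the strata. The documents do not support that under the current order of events, for the reason in step 6. That T1 follows disclosure is partly read from the order of the narrative, but no section requires T1 to come first. On this point the plan's choice to leave T1 out is the safer one.

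Finally, the power figures treat 104 patients per arm as complete. They do not model the planned multiple imputation and pattern-mixture analyses, or the loosening of stratum balance through attrition of up to 25%.

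**Conclusion.** The point holds as a low-cost improvement. The two stratification factors are missing from the primary model, and the generalizability argument does not justify leaving them out. The planned test remains unbiased and valid; a reader who infers that the omission invalidates it would be wrong.

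The benefit lies between nothing and a few points of power: up to about 7 points at R² = 10% and D near 0.50, both assumed. Adjustment does not rescue the stated 0.20 SD difference and is not needed at f² = 0.20 with 208 patients. The gap between those two effect sizes is a separate and larger sample size question that covariates do not solve.

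**What to change.** In Section 11.0, add the two T0 factors, dichotomized as in Section 12.3, as main effects to the primary MANOVA and to its IMCP versus ISP and IMCP versus EUC contrasts. Add them also to the MANCOVA of change scores for the moderator aim. Settle this before any unblinded analysis.

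The cost is one line of wording and 2 error degrees of freedom. No new data, visits or patient burden are involved, since both values are needed to randomize.

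Do not add the T1 scores to the primary model while T1 follows disclosure of the arm. Moving T1 ahead of disclosure would change trial conduct; it is a separate question and not part of this fix.

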All patients with solid tumors with advanced disease receiving ambulatory care at MSKCC and its affiliates are eligible for participation. Recruitment of patients will take place at MSKCC, in ambulatory care areas treating solid tumors (i.e., prostate, breast, lung, colorectal, hepatobiliary, head and neck cancers, and palliative medicine) or through the mail using letter recruitment. Potential subjects for the study will be identified, by the research staff and participating oncology staff, by cancer diagnosis and stage. Potentially eligible patients will be administered the Distress Thermometer (DT), in order to determine whether the patient meets the requisite threshold for study participation in person or over the telephone. Patients who indicate a 4 or greater on the DT will be offered participation and randomized to one of the two 7-session interventions (IMCP or ISP) or to the EUC control condition. The Individual Meaning Centered Psychotherapy (IMCP) intervention will focus on enhancing meaning and purpose in patients' lives. The Individual Supportive Psychotherapy (ISP) intervention will focus on helping patients cope with cancer and express their feelings about it. In Enhanced Usual Care patients will be given targeted referrals based on screening and will receive psychoeducational materials. All participants will complete assessment batteries consisting of self-report questionnaires which will be administered at four time points: Baseline (T1, week 1), mid-way through the intervention (Midpoint (T2), week 4-7), immediately

following the last session of the intervention (Post-intervention (T3), week 7-14), and at post intervention (Follow-up (T4), 8-12 weeks post T3 assessment).

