Following informed consent, patients will be assigned a subject number and randomized to one of the two 7 session interventions (IMCP vs ISP) or to the EUC control condition. Randomization will be completed by MSKCC's Department of Biostatistics. After randomization, participants will be contacted and informed which randomization assignment they received and scheduled for the intervention. The intervention should begin within four weeks of randomization. Patients who cannot begin the intervention within 30 days of consent (because of conflict or illness), will be placed on a waitlist so they can be offered the intervention when they do not have any conflicts at which time patients will be re-consented.

After the patient has been randomized, they will complete a T1-Baseline Assessment (week 1) before the 1st session (see Appendix C). The assessment battery will be re-administered at 3 subsequent points: T2 (midpoint, at session 4, Appendix D); T3 (post-intervention, following the 7th session of the intervention or at the completion of 14 weeks, whichever occurs first, Appendix E) to assess changes over the course of treatment; and T4 (follow-up, 8-12 weeks post completion of T3, Appendix F) to assess maintenance of treatment gains. The EUC sample will also be administered the battery of questionnaires at approximately equivalent intervals. Please see Appendices A, C, D, E, & F and if it is overly burdensome to come to the counseling center for assessments patients will be given the option to complete them by mail, email the blank questionnaires to participants for them to print and complete at home (forms will be returned by mail), or administer the questionnaires over the phone. Figure 3, section 9.0 for specific measures)

All intervention sessions will be conducted at Ambulatory Counseling Center facilities of the MSKCC Department of Psychiatry and Behavioral Sciences or another Memorial Sloan-Kettering Cancer Center treatment facility. However, in rare circumstances if deemed appropriate by the interventionist (e.g., illness, emergency, transportation difficulties) telephone sessions will be permitted. All psychotherapy sessions will be audio recorded to be used for treatment integrity purposes. Portions of these audio recordings may be transcribed for academic, educational, or

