The T2 (mid-intervention) assessments are made because some patients may be too sick to complete the 7-session intervention. For these patients, we will use the T2 assessment to represent the most available data on intervention effect.

Sample size and statistical power considerations:

Two important hypotheses need to be established in this trial: 1) IMCP is superior to EUC; and more importantly, 2) IMCP is superior to ISP for improving psychosocial outcomes in patients with advanced cancer. Therefore, we have based sample size considerations on sufficient statistical power to detect these two differences. We have conservatively based our sample size calculations on a 0.20 standardized mean difference in the MANOVA canonical variates between the IMCP and ISP interventions. This 0.20 difference is what Cohen would consider a —small effect size in psychosocial research (Cohen, 1992), representing subtle group differences typically observed in psychotherapy clinical trials. Cohen (1992) distilled the findings of decades of psychosocial research and arrived at a classification of a —small effect (0.20 standardized mean difference), a —medium effect (0.50 difference), and a —large effect (0.80+ difference). This —small difference is also a sensible assumption, due in part to the small group differences in some of the psychosocial outcomes in our pilot IMCP trial (Table 1, e.g., psychological distress). Thus, we planned to have a sufficiently large sample size to detect subtle differences. Overall, this conservative estimate would accommodate outcomes in psychological distress which our pilot data showed a small difference. Based on these assumptions, we would need 104 participants in each arm at post-intervention (week 7) in order to obtain a power of 0.80. Other assumptions that go into this estimation included two *a priori* contrasts (IMCP vs. EUC and IMCP vs. ISP), and a two-sided, type-I error rate of 0.01 in the MANOVA test. The statistical power calculations were obtained from the computer program G*Power version 3.1 (Faul, Erdfelder, Lang & Buchner, 2007), for a MANOVA model with six correlated outcome variables. The output of the G*Power estimate is included below.

F tests – MANOVA: Global effects

Options : Pillai V, O'Brien–Shieh Algorithm

Analysis : A priori: Compute required sample size

Input:	Effect size $f^2(V)$	= 0.20
	α err prob	= 0.01
	Power (1– β err prob)	= 0.80
	Number of groups	= 2
	Response variables	= 6

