Intent-to-treat (ITT) analysis is the gold standard in evaluating the relative efficacy of therapeutic regimes for patients assigned to different treatment arms whether or not they comply with the full treatment plan as defined in the protocol. In contrast to studies that assess clinical outcomes that are observable whether or not patients comply with therapy, it is likely in this study that patients who fail to participate in particular counseling sessions will also be missing the corresponding outcome data. Thus, examination and imputation of incomplete data will be an integral part of our ITT analysis. Data for intermediate time points might be imputable by one of several available statistical techniques. However, it is more problematic to assess outcomes for patients who essentially drop out of the study, namely, who are missing the final (and possibly preceding) evaluations. Although we shall endeavor to obtain final evaluation-time data even for patients who discontinue the counseling, but because of the likelihood that premature withdrawal is related to deteriorating physical health, we cannot rely on this and will therefore use appropriate statistical methods. One preferred approach is the Pattern-Mixture Model (Hedeker & Gibbons, 1997), which assumes that patients can be grouped into a small number of implicit cohorts with different patterns of missing data. This method models the trajectories of responses within each cohort and combines results across cohorts to make overall comparisons between treatment arms. The Pattern-Mixture Model can be relatively easily applied in practice using a publicly accessible SAS macro. This approach will handle two potential, inter-related issues, namely, intent-to-treat analysis and missing data while making a global assessment of the overall efficacy of the two types of counseling. We anticipate that the majority of patients will complete most or all of the planned sessions and the corresponding assessments. However, our pilot data suggest that there may be sufficient attrition to warrant use of the above-described approach even if drop-out rates do not differ significantly between the two treatment arms.

Missing data:

Because attrition may significantly impact the MANOVA, we will utilize several techniques for dealing with missing data (Nich & Carroll, 1997; Singer & Willett, 1991). These techniques may

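### The rule that uses T2 scores for patients too sick to finish seven sessions is not tied to a missing T3, cannot apply to EUC as worded, and is not placed among the planned missing-data methods

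*Combined protocol and SAP*

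**What the plan says.** Section 11.0 (Omnibus MANOVA for the primary aim) takes the six primary scales at the post-intervention time point, week 7, as dependent variables. The text under that heading ends by explaining that T2 is collected because "some patients may be too sick to complete the 7-session intervention", and continues: "For these patients, we will use the T2 assessment to represent the most available data on intervention effect".

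The assessment schedule is as follows.

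- **T2.** Section 1.0 places it "mid-way through the intervention (Midpoint (T2), week 4-7"; section 4.2 places it at session 4.
- **T3.** Section 4.2 sets it "following the 7th session of the intervention or at the completion of 14 weeks, whichever occurs first".
- **Nominal timeline.** The table in section 9.1 shows T2 at week 4 and T3 at week 7.
- **EUC.** Section 4.2: "The EUC sample will also be administered the battery of questionnaires at approximately equivalent intervals".

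The intent-to-treat text in section 11.0 expects that "patients who fail to participate in particular counseling sessions will also be missing the corresponding outcome data". It also says that "we shall endeavor to obtain final evaluation-time data even for patients who discontinue the counseling", and it considers it likely that "premature withdrawal is related to deteriorating physical health". That text calls the pattern-mixture model one preferred approach. The missing-data text then plans multiple imputation, a comparison with patients who completed the study, and an analysis that may assume no change in those who dropped out of treatment. Neither text mentions the T2 rule.

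**The concern.** There are three gaps in one rule.

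1. **Trigger.** The rule turns on not finishing the sessions because of illness. It does not turn on T3 being absent, and the plan's own definition of T3 lets a patient have one without seven sessions.
2. **Arms.** EUC has no sessions, so no EUC patient can meet the trigger, although EUC is assessed at T2 and T3 as well.
3. **Rank.** A patient filled in with T2 no longer counts as missing. Whether T2 is substituted before imputation, used inside it, or kept for a sensitivity analysis therefore decides which records the other methods act on.

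Two analysts following the plan could build different primary datasets. All change after T2 is lost for the substituted patients. Losing a late decline in the therapy arms would favour therapy over EUC; losing a late gain would work against it.

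**Working it through.** **The plan's own figures.** The plan gives no figure for the substituted share or for T2-to-T3 change. The nearest is attrition: 138 × (1 − 0.25) = 103.5, which matches the 104 per arm at T3. It does not say how many of those lost would have a T2.

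**Which value enters the primary dataset?** Three patients, under the text as written:

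| Patient | T2 rule | Other methods in section 11.0 |
|---|---|---|
| IMCP or ISP, stops after session 5 through illness, T3 obtained at 14 weeks | T2 (literal reading) | Observed T3 |
| IMCP or ISP, same but no T3 | T2 | Imputed, pattern-mixture, excluded, or no change |
| EUC, too ill for T3, T2 available | Does not apply | Imputed, pattern-mixture, excluded, or no change |

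The first row has two candidate values and the second has five. The second and third rows differ only by arm.

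**Length of the carry-forward.** Nominal timeline (section 9.1): 7 − 4 = 3 weeks. If the patient never reaches session 7, T3 is due at 14 weeks, and with T2 in week 4 to 7 the gap is 14 − 7 = 7 to 14 − 4 = 10 weeks.

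**Share that could be substituted, from the pilot (section 3.0).** Of 59 who began IMCP, 39 attended all seven sessions; the mean was 5.28.

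- Total sessions: 59 × 5.28 = 311.5. Completers used 39 × 7 = 273, leaving 38.5 for 20 others.
- If T2 requires session 4, at most 38.5 / 4 = 9.6, so 9 patients: 9/59 = 15.3%.
- No whole-number total over 59 gives exactly 5.28; 317/60 does. Then (317 − 273)/4 = 11, and 11/60 = 18.3%.
- Requiring the reported SD of 2.6 as well (2.55 to 2.65) leaves 8 or 9 of 59, and 11 of 60.

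These caps count non-completion for any reason; the rule covers illness only. The same section says over 90% received the full dose, which would put the share below 10% and conflicts with its own 66.1%. The pilot had no midpoint assessment.

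**Illustrative bias, IMCP vs EUC.** Bias = share × hidden decline, minus whatever is hidden in EUC. Assumed, not in the documents: share 15%, decline 0.2 to 0.5 SD.

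- None hidden in EUC: 0.15 × 0.2 = 0.03 to 0.15 × 0.5 = 0.075 SD.
- Half as much hidden in EUC: 0.015 to 0.0375 SD.
- Equal in EUC: 0.
- At the 18.3% cap: 0.183 × 0.5 = 0.09 SD, so 0.075 is not a maximum.

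**Effect on the omnibus test.** Simulated Pillai MANOVA with 3 × 104 patients, six outcomes, alpha 0.01, an assumed correlation of 0.5, both therapy arms shifted equally and no true effect. Rejection is about 1.0% to 1.3% at 0.0375 SD or less. At 0.075 SD it is about 1.4% to 1.6% if all six scales shift, and about 2.0% to 2.3% if three shift (range over repeated simulations).

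**IMCP vs ISP.** The equal-shift simulation says nothing about this contrast. An assumed 5-point difference in share with a 0.3 SD decline gives 0.05 × 0.3 = 0.015 SD.

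**The case against.** The strongest defence is that the sentence was meant as a fallback and would be used as one. It speaks of the most available data. The intent-to-treat text expects missed sessions and missing outcomes to go together. Section 10.0 takes patients who cannot tolerate the intervention off the protocol, so T3 will usually be absent. This largely stands. A reader might infer that the plan intends to overwrite observed T3 scores; the documents do not support that. What remains is a missing clause, and it matters because the same section promises to seek final data after counseling stops.

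The EUC limb also rests on wording. T2 is collected in EUC too, and section 11.0 counts EUC among its three interventions. The pattern-mixture text refers at one point to two types of counseling but elsewhere to treatment arms in general. A deliberately arm-specific rule should not be inferred. The reference to seven sessions nevertheless excludes EUC as written.

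A reader might also take the pilot's 33.9% non-completion (20 of 59) as the substituted share and derive a large loss of effect or power. That does not hold: many of those patients cannot have reached session 4, and the figure covers every reason for stopping.

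Finally, every bias figure rests on assumed inputs. That is correct, and the point does not depend on them.

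**Conclusion.** The point holds as a gap in the specification of the primary dataset, together with a weak method if the rule is used as the fallback it probably is. A single mid-treatment score is carried forward in patients whom the plan itself expects to be deteriorating, and the plan already contains a better use for T2.

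It does not hold as a claim of substantial or directional bias. Size and direction cannot be derived, because the documents give no T2-to-T3 change. Under the assumptions shown, the distortion of IMCP vs EUC is a few hundredths of an SD, and it shrinks to the extent that the same decline is hidden in EUC. For IMCP vs ISP, which the plan calls the more important hypothesis, bias arises only if the substituted share or the T2-to-T3 change differs between those two arms.

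Confidence is high for the wording gap and low for any bias figure. This is a cheap improvement.

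**What to change.** Replace the T2 sentence in section 11.0 with:

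> The primary analysis uses the observed T3 for every randomized patient who has one, whatever the number of sessions attended. Where T3 is missing, T2 is not substituted; it enters with T1 and other already collected predictors (such as screening Karnofsky and the Distress Thermometer at T0 and T2) in the planned multiple imputation, applied identically in all three arms. The pattern-mixture model in all three arms, and T2 substitution in all three arms, are sensitivity analyses.

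Multiple imputation assumes that missingness is explained by observed data, so the pattern-mixture model is a useful check on health-related dropout. The team may instead make the pattern-mixture model primary, provided one method is named and applied in all arms.

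Two additions are needed. State how patients who die before T3 are handled, since section 14.3 treats death as an expected event. Reconcile the Karnofsky entry in section 7.1, which says both that it is rated at each assessment and that it is collected at T0, T3 and T4, before relying on Karnofsky at T2.

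The cost is a few sentences and one team decision, with no new data or methods. Standard errors would be slightly larger: 1/√(1 − 0.15 × (1 − 0.7²)) = 1/√0.9235 = 1.04, about 4%, assuming 15% imputed and a T2–T3 correlation of 0.7.
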